Patient Population:

Patients with estrogen and/or progesterone receptor positive, HER2-negative advanced (metastatic) breast cancer that are in one of the following populations

Pre-menopausal Women:

- A. Pre-menopausal women who received adjuvant Aromatase Inhibitor and Ovarian Suppression (AI + OS) in the adjuvant setting and completed at least 12 months of hormonal therapy.
- B. Pre-menopausal women who have never been treated with endocrine therapy with de-novo metastatic disease.
- C. Pre-menopausal women who have not received Tamoxifen in the metastatic setting, but have received up to two lines of chemotherapy for dose expansion and up to three lines for dose escalation.

Post-Menopausal Women or Men

- D. Post-menopausal women or men who have progressed on first-line or second-line therapy with an aromatase inhibitor
- E. Post-menopausal women or men who have recurred while on or after completion of adjuvant treatment with aromatase inhibitors (they have completed at least one year of adjuvant AI in the adjuvant setting before progression on AI).
- F. Post-menopausal women or men who are not considered candidates for treatment with an aromatase inhibitor by their oncologist, refused AI, or intolerant to AI
- G. Post-menopausal women or men who have been treated with up to two lines of chemotherapy for dose expansion and up to three lines for dose escalation in the metastatic setting.

Total number of patients: 40

Number of Centers: 1 (will be adjusted, increased if accrual goals are not met).

Sample Size Justification (will be updated by statistician):

For a total of **40 subjects**, about 9-12 will be accrued during phase 1 portion and **about 30 patients for the phase 1b expansion.**

Part 1: phase 1 portion:

We will evaluate the first 9-12 patients in the phase I portion for safety.
The Primary objective is safety.

Part II: phase Ib expansion:

For the phase one expansion we will include pre- menopausal women, post-menopausal women, and men evaluated as one group. We will further evaluate both a three weeks on and one week off cohort (i.e. once daily for 21 consecutive days followed by a 7-day planned break) and a *continuous dose cohort* of ribociclib administered daily (QD) without a break in each cycle. Tamoxifen will be administered daily per standard of care in both cohorts.

The **primary objective** in the phase I study is to confirm safety, tolerability, confirm DLT, and determine the RP2D of Ribociclib with Tamoxifen

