10 STATISTICAL CONSIDERATIONS

10.1 Statistical Considerations for Phase I Study

A standard 3+3 design will be used (33) for the primary toxicity study under Phase I. A cohort of 3 patients will be recruited for each dose level at a time at a time. The first dose level will be level 1 and gradually increased to Level 2 and 3 if toxicity AEs are observed within the predefine statistical criterion/limit below.

Level 1: Ribociclib PO starting at a dose of 400 mg po for 21 days, followed by 1 week break of a 28-day treatment cycle;

Level 2: Ribociclib PO treated with a dose of 400 mg po daily for 28 days;

Level 3: Ribociclib PO treated with a dose of 600 mg po for 21 days, followed by 1 week break of a 28-day treatment cycle

If 1 patient out of 3 experiences a dose limiting toxicity (DLT; see below for definition) at level 1, 3 additional patients will be recruited at that dose level. If only 1 out of 6 patients in that dose level experiences a DLT, a new cohort of 3 patients will be treated with the next escalated dose level. That is, the dose escalation continues until at least two patients among a cohort of three to six patients experience dose-limiting toxicities (i.e., $\geq 33\%$ of patients with a dose-limiting toxicity at that dose level). If 2 out of 3 or 2 out of 6 patients experience a DLT, no further dose escalation will occur. The recommended phase II dose (RP2D) is defined as the dose level at which $\leq 1/6$ patients experience DLT. There will be no dose escalation beyond dose level 3, meaning that if $\leq 1/6$ patients experience DLT at this level, dose level will become the RP2D. No intra-patient dose escalation is allowed. Our dose escalation schedule follows a modified Fibonacci sequence in which the dose increments become smaller as the dose increases (e.g., the

dose first increases by 100% of the preceding dose, and thereafter by 50%, 33%, and 25% of the preceding doses). The RP2D will be defined as the dose level just below this toxic dose level.

Patients who achieve complete response (CR) or partial response (PR) or have stable disease (SD) may continue on study treatment until disease progression, as defined by RECIST v1.1 criteria, or intolerable toxicity.

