10.2 Statistical Considerations for Phase Ib Dose expansion Study

If no MTD is observed with Level 1 through 3, we plan to continue/conduct the phase Ib dose expansion study as below. This expansion study is planned to understand and obtain initial efficacy data for the secondary endpoints.

Since the identical patient inclusion/exclusion criteria will be used in phase Ib dose expansion, all patient data from phase I dose escalation and phase Ib dose expansion studies can be combined for our statistical analysis, therefore, the required sample size of patients below will be both for phase I dose escalation and phase Ib dose expansion studies.

We obtained our statistical power and required sample size as a single-arm prospective study. In particular, for our evaluation of early efficacy we designed the study particular, for our evaluation of early efficacy we designed the study for testing $H_0: P \leq 0.10$ versus $H_1: P \geq 0.25$ at one-sided significance level 0.05 and power 0.80 as below.

P0	P1	Alpha	Beta	Cut-Off		Actual	Actual
				R + 1	N		
0.100	0.250	0.050	0.200	8	40	0.042	0.182

Where P0 is the maximum response proportion of standard care (tamoxifen alone), P1 is the minimum response proportion of our experimental treatment group, and N is the sample size.

For our statistical testing, if the number of responses $\geq R+1$, P0 is rejected based on Fisher's Exact test (34, 35). Alpha is the probability of rejecting that $P \leq P_0$ when this is true.

Beta is the probability of rejecting that $P \geq P_1$ when this is true.

Thus, the study requires 6 subjects under phase I dose escalation and 30 subjects under phase Ib dose expansion who will be treated with ribociclib (total 36) in order to test whether the proportion responding, P, is less than or equal to 0.100 or greater than or equal to 0.25. If the number of responses is 8 or more, the hypothesis that $P \leq 0.100$ is rejected with a target Type I error rate, α , of 0.050 and an actual error rate of 0.045. The null hypothesis will be rejected if 8 or more responses are observed in 40 patients. This design yields a type I error rate of 0.045 and power of 0.818 when the true response rate is 0.25.

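### Section 10.2 gives two sample sizes (36 and 40) and two type I errors (0.045 and 0.042) for one response test; only 8 of 40 with 0.042 meets the stated targets

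*Combined protocol and SAP*

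**What the plan says.** Section 10.2 tests a response rate of at most 0.10 against at least 0.25, at one-sided level 0.05 with power 0.80. The design table gives a cut-off of 8, N = 40, actual alpha 0.042 and actual beta 0.182. The section ends with the rule "The null hypothesis will be rejected if 8 or more responses are observed in 40 patients". The Synopsis agrees on the size: "Total number of patients: 40".

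Other statements in Section 10.2 do not fit this:

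- The required number is given as "6 subjects under phase I dose escalation and 30 subjects under phase Ib dose expansion who will be treated with ribociclib (total 36"), followed by the same cut-off of 8.
- The type I error appears as "an actual error rate of 0.045" and again in "This design yields a type I error rate of 0.045 and power of 0.818 when the true response rate is 0.25".
- The two phases are pooled on the ground that "Since the identical patient inclusion/exclusion criteria will be used in phase Ib dose expansion".

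On escalation numbers, the Synopsis says "about 9-12 will be accrued during phase 1 portion and" about 30 in the expansion. Section 10.1 says "A cohort of 3 patients will be recruited for each dose level at a time", and Table 8-1 in Section 8.1 lists three levels of 3 to 6 patients plus two expansion cohorts of 15.

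**The concern.** This is the only formal hypothesis test in the plan, and its sample size, error rate and population are each stated in ways that conflict. A reader who takes 36 as the requirement would run a test with less power than the 0.818 quoted beside it. The figure of 0.045 disagrees with the table a few lines above.

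The number analysed is also left open. Six escalation patients do not fit three levels of at least three. Six could mean only the two regimens that are expanded, but the text does not say so. The only cut-off is for 40, and nothing says it is recomputed if another number is analysed.

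Finally, the eligibility criteria behind the pooling are not identical. Section 4 (Shared Eligibility) allows bone-only disease and three chemotherapy lines in escalation, against measurable disease and two lines in expansion.

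**Working it through.** **Inputs (Section 10.2).** P0 = 0.10, P1 = 0.25, one-sided alpha 0.05, power 0.80, cut-off c = 8, N = 40 (table and closing rule) or 36 (text).

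**Formula.** For N patients and cut-off c, the rejection probability is P(X ≥ c | N, p) = Σ from k = c to N of C(N,k) p^k (1−p)^(N−k). Alpha is this tail at p = 0.10 and power is the tail at p = 0.25.

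**Step 1: reproduce the table.** At N = 40, c = 8, alpha = 0.0419 and power = 0.8180, so beta = 1 − 0.818 = 0.182. The table is right.

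**Step 2: apply the text's 36.**

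| N | c | alpha | power |
|---|---|---|---|
| 36 | 7 | 0.063 | 0.832 |
| 36 | 8 | 0.024 | 0.710 |
| 39 | 8 | 0.037 | 0.794 |
| 40 | 8 | 0.042 | 0.818 |

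At 36, a cut-off of 7 breaks the alpha limit and 8 misses the power target by 0.80 − 0.710 = 0.090. A search over every N from 5 upward and every cut-off finds N = 40, c = 8 as the first pair meeting both targets.

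**Step 3: the figure 0.045.** No pair with N from 20 to 60 and c from 3 to 14 has an exact alpha that rounds to 0.045. At N = 40, c = 8, other methods give 0.0175 (normal), 0.0325 (normal with continuity correction), 0.0511 (Poisson) and 0.0567 (two-sided exact). None gives 0.045.

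**Step 4: how many could be analysed.** Three levels of 3 to 6 give 9 to 18. Adding two cohorts of 15 gives 39 to 48. The Synopsis range gives 9 + 30 = 39 to 12 + 30 = 42. Section 8 makes the continuous cohort conditional on tolerability; if it did not open, the total would be 9 + 15 = 24 to 18 + 15 = 33. These counts are before any replacement of patients.

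**Step 5: keep c = 8 at larger N.**

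| N | alpha | power |
|---|---|---|
| 41 | 0.048 | 0.839 |
| 42 | 0.054 | 0.859 |
| 45 | 0.076 | 0.906 |
| 48 | 0.102 | 0.939 |

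**Step 6: the smallest c with exact alpha ≤ 0.05.**

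| N | c | alpha | power |
|---|---|---|---|
| 24–27 | 6 | 0.028–0.047 | 0.578–0.701 |
| 28–34 | 7 | 0.018–0.048 | 0.572–0.782 |
| 35–41 | 8 | 0.020–0.048 | 0.678–0.839 |
| 42–48 | 9 | 0.021–0.046 | 0.757–0.881 |

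Under this rule power is below 0.80 at every N up to 39 (for example 0.652 at 30) and again at 42 (0.757) and 43 (0.783).

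**Step 7: who is in the denominator.** For expansion, Section 4 requires measurable disease. Section 8.6, on the expansion cohorts, accepts a lytic bone lesion where there is none. Section 11.1.2 classes bone lesions as non-measurable, while Section 11.6 admits bone-only disease if a lesion is measurable on MRI. For escalation, Section 4 admits bone-only disease outright. The documents do not say whether such patients count in the 40.

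**The case against.** The strongest reply is that this is an editorial slip. The table, the closing rule, the power of 0.818 and the Synopsis total all say 40, so one sentence is the outlier. Anyone who did use 8 of 36 would err conservatively (alpha 0.024), and 0.045 against 0.042 is below 0.05 either way. This is fair and is why the point is not graver. It does not make 36 correct: the sentence states it as a requirement, built from its own two components, and it fails the power target.

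The range of totals can also be challenged. The Synopsis says that a continuous arm found too marrow suppressive switches schedule, so the arm would not be lost for that reason. Two dose-limiting toxicities at level 2 would stop escalation before level 3, and Section 10.2 plans the expansion only if no MTD is found. The 24 to 33 case is therefore narrow. At the other end, 48 needs all three levels filled to six. Both remain possible as written, and 42 lies within the Synopsis's own range.

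Section 11.3 requires replacement of patients unevaluable for response, which helps hold the number. It covers early death and absence of any follow-up assessment, not bone-only patients enrolled in escalation.

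The Synopsis does state the chemotherapy-line difference openly. Section 10.2 nonetheless pools on the premise of identical criteria.

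**Conclusion.** The concern holds. The design of 8 or more responses in 40 is sound and is the smallest that meets the stated targets. The required size of 36 is wrong for that design: power would be 0.710, which is 0.818 − 0.710 = 0.108 below the power quoted. The type I error of 0.045 is wrong in both places and should be 0.042. With no cut-off for other sizes, using 8 unchanged exceeds one-sided 0.05 from 42 patients and reaches 0.102 at 48. These results assume an exact one-sample binomial test with the plan's own rates and a single pooled analysis. The practical effect is modest, since response is secondary and the alpha discrepancy alone changes no decision, but the section should be corrected.

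**What to change.** 1. Keep 40 patients and 8 or more responses as the design basis. Reconcile the six escalation patients and the total of 36 with the 9–12 and 40 in the Synopsis. If six means only the two expanded regimens, say so and do not call 36 the required size.
2. Change 0.045 to 0.042 in both places.
3. Define the response-analysis population. Reconcile Sections 4, 8.6, 10.2, 11.1.2 and 11.6 on measurable and bone-only disease, and replace the claim of identical criteria.
4. State that the cut-off is the smallest count with exact one-sided alpha ≤ 0.05 at the number analysed: 6 for 24–27, 7 for 28–34, 8 for 35–41 and 9 for 42–48. Report the power at that number.
5. As a wording correction only, name the test as the one-sample exact binomial rather than Fisher's exact test.

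The cost is wording in Section 10.2 and its cross-references, with no extra patients. The drawback is that less favourable power must be reported at some sizes, for example 0.794 at 39 and 0.757 at 42.

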10.3 Statistical Considerations for Safety

Toxicity assessment, interim history and physical exam, CBC and chemistry profile weekly in cycle 1, then at day 1 of each cycle for the first 6 months and at least every 2 cycle thereafter. Adverse Events and other symptoms will be assessed continuously and graded according to the NCI Common Toxicity Criteria Version 4.03. Patients will be followed for evaluation of safety for at least 30 days after the last dose of study drug. Any study drug-related serious adverse events will be followed until resolution, return to baseline grade, or deemed irreversible by the Investigator.

In this protocol, the routine use of any and all anti-emetics is allowed as clinically appropriate; these include the use of dexamethasone and 5-HT3 receptor antagonists.

11 CRITERIA FOR RESPONSE, PROGRESSION AND RELAPSE

Response and progression will be evaluated in this study using the new international criteria proposed by the Response Evaluation Criteria in Solid Tumors (RECIST 1.1) Committee. (15) Changes in only the largest diameter (unidimensional measurement) of the tumor lesions are used in the RECIST 1.1 criteria. Note: Lesions are either measurable or non-measurable using the criteria provided below. The term “evaluable” in reference to measurability will not be used because it does not provide additional meaning or accuracy.

For the purposes of this study, patients should be evaluated for response every 8 weeks. In addition to a baseline scan, confirmatory scans should also be obtained ≥ 4 weeks following initial documentation of objective response.

11.1 Criteria for Target Lesions

11.1.1 *Measurable disease*

Measurable lesions are defined as those that can be accurately measured in at least one dimension (longest diameter to be recorded) as ≥ 20 mm with conventional techniques (CT, MRI, x-ray) or as ≥ 10 mm with spiral CT scan. All tumor measurements must be recorded in millimeters (or decimal fractions of centimeters).

11.1.2. *Non-measurable disease*

All other lesions (or sites of disease), including small lesions (longest diameter < 20 mm with conventional techniques or < 10 mm using spiral CT scan), are considered non-measurable disease. Bone lesions, leptomeningeal disease, ascites, pleural/pericardial effusions, lymphangitis cutis/pulmonis, inflammatory breast disease, abdominal masses (not followed by CT or MRI), and cystic lesions are all non-measurable.

11.1.3. *Target lesions*

- All measurable lesions up to a **maximum of two lesions per organ** and **five lesions in total**, representative of all involved organs, should be identified as target lesions and recorded and measured at baseline.
- Target lesions should be selected on the basis of their size (lesions with the longest diameter) and be representative of all involved organs, as well as their suitability for reproducible repeated measurements.
- All measurements should be recorded in metric notation using calipers if clinically assessed. A **sum of the diameters (longest for non-nodal lesions, short axis for nodal lesions)** for all target lesions will be calculated and reported as the baseline sum diameters, which will be used as reference to further characterize any objective tumor regression in the measurable dimension of the disease. If lymph nodes are to be included in the sum, only the short axis will contribute.

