4 INCLUSION CRITERIA

A. Shared Eligibility

1. Histologically and/or cytologically confirmed diagnosis of ER+ and/or PR+ breast cancer by local laboratory.
2. HER2-negative breast cancer defined as a negative in situ hybridization test or an IHC status of 0, 1+ or 2+. If IHC is 2+, a negative in situ hybridization (FISH, CISH, or SISH) test is required by local laboratory testing.
3. Patients are allowed (but not required) to have up to **two** lines of prior chemotherapy regimens in the metastatic setting for the dose expansion phase (). For the dose escalation cohort, up to three previous lines of chemotherapy in the metastatic setting is acceptable.
4. Measurable disease, i.e., at least one measurable lesion as per RECIST 1.1 criteria only **for expansion cohorts**.

5. For **escalation cohorts**, bone only disease is allowed. For expansion cohorts, there must be measurable disease as stated above (#4)..
6. ECOG PS 0 or 1.
7. Written informed consent must be obtained prior to any screening procedures and according to local guidelines.
8. Patient has adequate bone marrow and organ function as defined by the following laboratory values:
 - a. Absolute neutrophil count $\geq 1.5 \times 10^9/L$.
 - b. Platelets $\geq 100 \times 10^9/L$.
 - c. Hemoglobin $\geq 9 \text{ g/dL}$.
 - d. Potassium, total calcium (corrected for serum albumin), magnesium, and sodium within normal limits for the institution or corrected to within normal limits with supplements before first dose of study medication
 - e. INR ≤ 1.5 .
 - f. Serum creatinine $\leq 1.5 \times \text{ULN}$ or creatinine clearance $\geq 50 \text{ mL/min}$
 - g. In the absence of liver metastases, alanine aminotransferase (ALT) and aspartate aminotransferase (AST) $< 2.5 \times \text{ULN}$. If the patient has liver metastases, ALT and AST $< 5 \times \text{ULN}$.
 - h. Total bilirubin $\leq \text{ULN}$; or total bilirubin $\leq 3.0 \times \text{ULN}$ or direct bilirubin in patients with well-documented Gilbert's Syndrome
9. Must be able to swallow ribociclib and Tamoxifen capsules/tablets

B. Pre-menopausal Women Eligibility

1. Premenopausal women who received adjuvant Aromatase Inhibitor and Ovarian Suppression (AI + OS) in the adjuvant setting and completed at least 12 months of hormonal therapy.
2. Pre-menopausal women with *de novo* metastatic disease are eligible if they have had no prior endocrine therapy.

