Other metastatic disease sites will be followed by CT or MRI, as clinically indicated. Chest x-ray or ultrasound should not be used to assess tumor lesions. Partial Response (PR) and Complete Response (CR) must be confirmed by repeat assessments performed not less than 4 weeks and after the criteria for objective response are first met. In case tumor assessment is performed <8 weeks from the first assessment of an objective response to confirm PR/CR, subsequent tumor assessments should revert back to the protocol schedule outlined in study calendar. At the discretion of the Investigators, FDG-PET scans may be performed to document progressive disease per RECIST 1.1 (see Appendix 1). If possible, a

single radiologist should perform all tumor response evaluations for an individual patient. Any lesions in previously irradiated areas should not be considered measurable unless they have experienced progression since the radiotherapy.

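### Lymph nodes qualify as measurable on longest diameter (11.1.1) but enter the baseline sum on short axis with no minimum (11.1.3), and eligibility points to a second rule

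*Combined protocol and SAP*

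**What the plan says.** For the expansion cohorts, criterion A.4 in section 4 requires "at least one measurable lesion as per RECIST 1.1 criteria only". Sections 8.6 and 11.6 likewise refer to RECIST 1.1 for what counts as measurable.

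The introduction to section 11 gives a different source: "Lesions are either measurable or non-measurable using the criteria provided below". Those criteria follow:

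- **11.1.1** defines a measurable lesion by a single size rule: "longest diameter to be recorded) as ≥ 20 mm with conventional techniques (CT, MRI, x-ray) or as ≥ 10 mm with spiral CT scan". Nodes are not treated separately.
- **11.1.2** is the complement. All remaining lesions, "including small lesions (longest diameter < 20 mm with conventional techniques or < 10 mm using spiral CT scan), are considered non-measurable disease".
- **11.1.3** picks targets by the same axis: "Target lesions should be selected on the basis of their size (lesions with the longest diameter". The sum then changes axis for nodes: "If lymph nodes are to be included in the sum, only the short axis will contribute". No smallest short axis is given.
- **11.2.1** defines PR (a fall of at least 30%) and PD (a rise of at least 20%) on the sum of longest diameters, with no exception for nodes.
- **11.4.1** gives palpable lymph nodes as an example of a measurable clinical lesion, so nodes are in scope.

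**The concern.** The axis that lets a node in as a target is not the axis on which it is scored. A node is longer than it is wide, so its scored size is the smaller of the two, and nothing in section 11 sets a floor. When the denominator of a percentage change is a few millimetres, ordinary reading variation can cross the PR or PD threshold. Section 11.4.2 specifies 5 mm reconstruction for spiral CT, which is as coarse as the smallest baselines at issue.

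The response rate is the only endpoint with a hypothesis test (section 10.2). Progression sets time to progression (3.2) and ends study treatment (8.7). A site must also decide whether eligibility follows RECIST 1.1 itself or the text of 11.1.1, and the plan does not say which prevails.

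**Working it through.** **1. The axes side by side**

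| Step | Section | Axis for a node |
|---|---|---|
| Eligible as measurable | A.4, 8.6, 11.6 | whatever RECIST 1.1 says; not printed |
| Classed measurable or not | 11.1.1, 11.1.2 | longest |
| Selected as target | 11.1.3 | longest |
| Entered in baseline sum | 11.1.3 | short, no minimum |
| Scored for PR and PD | 11.2.1 | longest, as worded |

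**2. What this does to the thresholds.** Node sizes are assumed, because the documents give none. The node is taken as the only target.

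| Node on spiral CT | 30% fall, short axis | 30% fall, longest | 20% rise, short axis | 20% rise, longest |
|---|---|---|---|---|
| 10 x 5 mm | 0.3 x 5 = 1.5 mm | 3.0 mm | 0.2 x 5 = 1.0 mm | 2.0 mm |
| 20 x 8 mm | 0.3 x 8 = 2.4 mm | 6.0 mm | 0.2 x 8 = 1.6 mm | 4.0 mm |

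Both nodes qualify under 11.1.1.

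**3. Chance of a false reading in truly stable disease.** Assume a sole nodal target of true short axis d, scored on short axis, with independent reading error of SD s at each scan. The documents give no s; I use 0.75, 1.0 and 1.5 mm. With baseline reading X and follow-up reading Y:

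- PR at the first follow-up: P(Y ≤ 0.7X) = Φ(−0.3d / (s√1.49)).
- PD at the first follow-up: P(Y ≥ 1.2X) = 1 − Φ(0.2d / (s√2.44)).

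For d = 5 and s = 0.75, the PR argument is 1.5 / (0.75 x 1.221) = 1.64, which gives 0.05.

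| d | First-scan PR, s = 0.75 / 1.0 / 1.5 | First-scan PD, s = 0.75 / 1.0 / 1.5 |
|---|---|---|
| 5 mm | 0.05 / 0.11 / 0.21 | 0.20 / 0.26 / 0.33 |
| 10 mm | 0.000 / 0.007 / 0.051 | 0.04 / 0.10 / 0.20 |
| 15 mm | 0.000 / 0.000 / 0.007 | 0.005 / 0.03 / 0.10 |

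PR has to be confirmed (8.6, 11). A simulation of 200,000 stable patients per setting, with six scans and PR on two consecutive scans before any 20% rise over the smallest value, gives a false confirmed PR at d = 5 in 0.021 / 0.053 / 0.098, or about 2% to 10%.

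**4. Effect on the response test.** First the plan's own figure. Rejecting at 8 or more responses in 40 has exact alpha P(Bin(40, 0.10) ≥ 8) = 0.0419 and power P(Bin(40, 0.25) ≥ 8) = 0.818. This matches the table in 10.2 (0.042; beta 0.182). The 0.045 in the text of 10.2 does not reproduce for this rule.

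Now let k of the 40 have a sole 5 mm nodal target (k is assumed), each with false confirmed PR probability f. Under the null each such patient counts as a responder with probability q = 1 − 0.9(1 − f), and alpha = P(Bin(k, q) + Bin(40 − k, 0.10) ≥ 8).

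| k | f = 0.021 (q = 0.119) | f = 0.098 (q = 0.188) |
|---|---|---|
| 1 | 0.043 | 0.047 |
| 2 | 0.044 | 0.052 |
| 4 | 0.046 | 0.063 |

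**The case against.** Much of the case on the other side stands.

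- **The scoring rule as worded is not short axis.** Section 11.2.1 says longest diameter. Scored that way, the 10 mm long node needs a 3 mm fall, and on the same error model the first-scan chance of PR is 0.05% to 5%, not 5% to 21%. The larger figures therefore assume that the 11.1.3 sum is what is scored. This limits the magnitude. It does not remove the conflict, because 11.1.3 defines the baseline sum that serves as the reference.
- **There are soft safeguards.** 11.1.1 wants lesions that can be measured accurately, 11.1.3 wants targets that can be re-measured reproducibly, and 8.6 asks for a single radiologist per patient where possible and for confirmation of response. They work against a 5 mm sole target but set no number, and no confirmation is required for PD.
- **The error model is harsh.** An SD of 0.75 to 1.5 mm is 15% to 30% of a 5 mm lesion. The same model labels at least about 43% of stable 10 mm targets as PD within six scans, so its output is illustrative.

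A reader might also infer several stronger points, which the documents do not support:

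- *That the 20/10 mm cut-offs depart from RECIST 1.1, or that calling a 10-19 mm lesion on MRI non-measurable is wrong.* The RECIST 1.1 thresholds are not printed in the protocol, so neither can be shown from it.
- *That admitting x-ray in 11.1.1 contradicts 8.6.* The bar there is narrower: "Chest x-ray or ultrasound should not be used to assess tumor lesions". Section 8.6 allows x-ray follow-up of skeletal lesions.
- *That 11.1.1 alone fixes the tested denominator.* Eligibility cites RECIST 1.1 directly, and the 40 in section 10.2 pool escalation patients, for whom bone-only disease is allowed.
- *That small nodal baselines will be routine.* No node sizes or frequencies are given.

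**Conclusion.** The point holds as an internal inconsistency. Nodes qualify and are selected on longest diameter, are summed on short axis without a minimum, and are scored in 11.2.1 on a sum worded as longest diameter. Two definitions of measurable disease are also in force, the one that A.4 cites and the one that section 11 writes out. None of this depends on an outside source.

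The effect on an individual patient can be material: about 2% to 10% for a false confirmed PR, given a sole 5 mm nodal target, short-axis scoring and the assumed reading error. The effect on the trial is modest, with alpha moving from 0.042 to about 0.043-0.063 if 1 to 4 of 40 patients are of this kind. That number of patients is an assumption. The correction is worth making because it is cheap and removes a choice from the sites. The figures do not show that the response test is invalid.

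**What to change.** In 11.1.1 and 11.1.2, qualify non-nodal lesions on longest diameter and lymph nodes on short axis, the axis that 11.1.3 sums. Take the minimum nodal short axis from the RECIST 1.1 standard that A.4 invokes and print it, so that eligibility and section 11 give one rule. Record nodes below that minimum as non-target. In the same edit, replace the longest-diameter sum in 11.2.1 with the sum of diameters defined in 11.1.3, and adjust the introductory sentence of section 11 ("Changes in only the largest diameter (unidimensional measurement) of the tumor lesions are used in the RECIST 1.1 criteria"). Changing 11.2.1 alone would not be enough: scoring would settle on the smaller axis while entry stayed on the larger one.

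The cost is wording only, with no change to sample size or visits. The downside is that a few patients whose only target would be a small node would not qualify for expansion.
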